8.1 Efficacy Assessments

Efficacy will be assessed through PASI, sPGA, BSA, Itch NRS, Skin Pain NRS, and participant-reported DLQI. Detailed instructions on collection methods for efficacy assessments are provided in the Study Reference Manual.

8.1.1 Participant-reported Outcomes (PROs)

In-clinic PRO assessments (DLQI, Itch NRS, Skin Pain NRS) must be completed before any other study assessments at each study visit except at Screening (refer to the Study Reference Manual). Participants must be given a quiet, private place to complete these assessments.

8.2 Safety Assessments

8.2.1 Physical Examinations

A full physical examination will involve assessment of the following: general appearance; ears, nose and throat; head, neck and thyroid; cardiovascular; dermatological, respiratory; lymph nodes; abdomen; musculoskeletal and nervous system.

A targeted physical examination will involve assessment of the following: cardiovascular; dermatological, respiratory; abdomen and, any other system if deemed necessary.

Any new or worsening changes from Baseline should be recorded as TEAEs, if appropriate.

8.2.2 Vital Signs

Vital signs include body temperature (ear or oral), respiratory rate, seated blood pressure, and heart rate. Blood pressure and heart rate should be measured after the participant has been resting quietly for \geq 5 minutes.

8.2.3 Body Weight, Height, and BMI

The participant's body weight and height will be recorded, and BMI will be calculated. Measurements will be taken in normal indoor clothing with shoes removed.

8.2.4 Electrocardiograms

12-lead ECGs will be measured after the participant has been in the supine position for a minimum of 5 minutes. Single 12-lead safety ECGs (Screening, Day 85/Early Termination, and Day 115 will be read by the Investigator to identify any clinically significant abnormalities that would exclude the participant from further study participation. Triplicate ECGs will be obtained approximately 1 minute apart at predose and at 1 hour after dosing on Days 1, 15, and 57. Blood draws should be avoided in the period immediately before ECG measurement and activity should be controlled as much as possible to minimize variability due to effects of physiologic stress.

8.2.5 Clinical Safety Laboratory Assessments

Available blood and urine sample results will be reviewed by the Investigator (or designee) before the participant is dosed on Day 1.

A list of the laboratory parameters measured is presented in Section 10.2.

8.2.5.1 Hematology, Clinical Chemistry, Coagulation, Urinalysis and Virology

Site standard collection and processing procedures for blood and urine samples will be adhered to throughout the study. Scheduled blood samples for fasting lipid panel and fasting glucose will be taken following a ≥ 8 hour fast (water is permitted). Laboratory tests will be performed by the central laboratory.

8.2.5.2 COVID-19 Antigen Test (nasal swab)

COVID-19 testing will be performed on site or by the site's local laboratory. Site standard collection and processing procedures for samples will be adhered to throughout the study.

8.2.5.3 Pregnancy Test

Pregnancy tests (urine dipstick and serum testing at Screening and urine dipstick testing only at all other time points) will be performed for all female participants of childbearing potential. Site standard collection and processing procedures for samples will be adhered to throughout the study.

8.2.5.4 Follicle Stimulating Hormone Test

Serum follicle stimulating hormone tests will be performed by the central laboratory to confirm postmenopausal status at Screening. Site standard collection and processing procedures for blood samples will be adhered to throughout the study.

8.2.5.5 Abnormal Laboratory Findings

In cases where laboratory findings are outside the normal range and the Investigator believes that the results may be of clinical significance, repeat sampling may be requested as clinically indicated. If the abnormal finding is clinically significant, appropriate actions will be taken (eg, the participant will not be entered into the study or the participant may be withdrawn from the study). The participant will be referred to their general practitioner or other appropriate provider for further care. The same will apply if the results of the HBsAg, hepatitis C virus antibody, or HIV test are positive and in addition the Investigator will ensure that adequate counselling is available, if requested.

Abnormal results at follow-up assessments will also require repeat testing if the Investigator believes the results may be of clinical significance (Section 10.4). Any clinically significant abnormality, including changes from Baseline (predose Day 1 or the last nonmissing value predose), should be reported as an AE.

Additional blood, urine, and/or throat swab samples may be taken for safety tests. Furthermore, additional assays outside those specified in the protocol may be performed for safety reasons as requested by the Investigator.

8.2.5.6 Columbia-Suicide Severity Rating Scale (C-SSRS)

The C-SSRS is utilized to prospectively assess and directly classifies suicidal ideation and behavior into 11 categories. The C-SSRS assesses lifetime and current suicidal thoughts and behaviors across these categories based on an increasing severity of a 1 to 5 rating scale. At the Screening visit, questions will be in relation to lifetime experiences. At all subsequent evaluations, the questions will be in relation to the last assessment. The C-SSRS 'Baseline/ Screening version is to be used at Screening and C-SSRS 'Since Last Visit' version is to be used for all other study visits. The C-SSRS will be completed by the Investigator or by a qualified designee.

8.2.6 Adverse Events

The definition of an AE can be found in Section 10.3. AEs will be reported by the participant (or, when appropriate, by a caregiver, surrogate, or the participant's legally authorized representative). The Investigator and any qualified designees are responsible for detecting, documenting, and recording events that meet the definition of an AE and remain responsible for following up AEs that are serious, considered related to the study drug or study procedures, or that caused the participant to discontinue study drug (Section 10.3).

8.2.6.1 Time Period and Frequency for Collecting AE Information

Investigators will seek information on AEs at each participant contact. All AEs, whether reported by the participant or noted by study staff, will be recorded in the participant's medical record and on the Adverse Event eCRF.

After **informed consent** has been obtained **but before initiation of study drug**, only SAEs caused by a protocol-mandated intervention (eg, invasive procedures such as biopsies, discontinuation of medications) should be reported (see Section 10.3.5 for instructions for reporting SAEs).

After initiation of study drug, all AEs will be reported until end of study at the Follow-up Visit or until an Early Termination visit.

Investigators are not obligated to actively seek AEs after conclusion of study participation. However, if the Investigator learns of any SAE, including a death, at any time after a participant has been discharged from the study, and he/she considers the event to be reasonably related (probable related or possible related) to the study drug or study participation, the Investigator must promptly notify the Sponsor.

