Safety will be evaluated by presenting summaries of AEs, vital signs, physical examination findings, ECGs, and clinical laboratory evaluations. Safety variables will be tabulated by DC-806 dose regimen and placebo.

Adverse events will be coded using the Medical Dictionary for Regulatory Activities (MedDRA®). The incidence proportion of TEAEs will be presented by system organ class and preferred term, by relationship to study drug, by severity, and by whether or not they resulted in alteration of administration of or discontinuation of study drug. A TEAE is defined as an AE that occurs during or after the first study drug administration and up to and including the Follow-up Visit. In addition, the incidence proportion of serious TEAEs and TEAEs leading to discontinuation of study drug will be presented by system organ class, preferred term, and relationship to study drug.

Vital signs and clinical laboratory test results will be listed and summarized by treatment. Any significant physical examination findings and clinical laboratory results will be listed. ECG readings will be evaluated by the Investigator and abnormalities, if present, will be listed.

[figure not shown]
Pharmacokinetic Analyses

Summary statistics will be tabulated for maximum observed concentration (C_{max}) or C_{trough} levels at different planned time points. Additional details will be provided in the SAP as necessary.

Pharmacodynamic Analyses

Serum concentrations of inflammatory cytokines (eg, IL-17 and IL-19 and potentially other IL-17 pathway and psoriasis biomarkers) and gene expression levels of multiple IL-17 pathway related markers in skin before and after DC-806 treatment will be analyzed as exploratory assessments. These analyses are outside the scope of the study SAP.

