- i. After informed consent has been obtained, but before initiation of study drug, only serious adverse events caused by a protocol-mandated intervention should be collected and reported to the Sponsor. After initiation of study drug, all adverse events will be collected and reported to the Sponsor until the last follow-up visit. In addition, the Sponsor must be notified of any serious adverse events the Investigator becomes aware of that has occurred after the last follow-up visit and that is believed to be related to study drug.
- j. Please refer to the Study Reference Manual for compliance thresholds.
- k. Vital signs include body temperature (ear or oral), respiratory rate, seated blood pressure, and heart rate. Blood pressure and heart rate should be measured after the participant has been resting quietly for ≥5 minutes. Temperature should be measured using the same methodology throughout the study. Participants must refrain from using tobacco, caffeine or xanthine-containing for 30 minutes before vital signs being recorded.
- 1. 12-lead ECGs should be recorded after the participant has been supine for ≥5 minutes. Safety ECGs will be read by the Investigator to determine any clinically significant abnormalities that would exclude the participant from further study participation (Section 5.2).
- m. 12-lead ECGs will be performed in triplicate, after the participant has been supine for ≥5 minutes, approximately 1 minute apart at predose and at 1 hour after dosing on Days 1, 15, and 57.
- Please refer to the Study Reference Manual.
- o. Skin biopsies are to be performed on Day 85 and are not required at the ET visit but may be collected at Investigator's discretion.
- p. Participants are required to fast for ≥8 hours before the collection of specimens.
- q. Serology includes HCV Ab, HBsAg, HBsAb, HBcAb, and HIV-1 and HIV-2 antibodies. Participants who are HBsAg negative, HBcAb positive, and HBsAb positive at Screening will have reflex testing for HBV DNA. Participants who are HCV Ab positive will have reflex testing for HCV RNA.

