Participants with active suicidal indication as indicated by a positive response ("Yes") to Question 4 of the "Since Last Visit" version of the C-SSRS must be referred immediately to a mental health professional and may be withdrawn from the study based upon the Investigator's judgment.

The mental health consultation must be recorded in source documentation.

- Confirmed OTcF interval of >500 ms
- Pregnancy
- Significant deviation from the protocol that is considered, in the opinion of the Investigator
 or Sponsor, to jeopardize the participant's safety
- Requirement for prohibited medication
- Upon the participant's request (withdrawal of consent)
- At the discretion of the Investigator or Sponsor
- Termination of the study for any reason by the Sponsor

Participants who prematurely discontinue study drug treatment due to an AE or laboratory abnormality should continue to be followed for all regularly scheduled visits as outlined in Section 1.3, and adhere to all study procedures (except for dispensing study drug, efficacy and participant-reported outcomes assessments, PK/PD sample collection, and skin biopsies [if applicable]) until the AE or laboratory abnormality resolves or stabilizes, unless they have decided to discontinue the study participation entirely (withdrawal of informed consent).

For a participant who prematurely discontinues study drug, every effort will be made to ensure the participant completes Early Termination procedures (if applicable) as soon as possible after discontinuation of study drug and as detailed in the study Schedule of Assessments (Section 1.3). The scheduled safety follow-up visit will also be performed, if possible, if the Early Termination visit has been performed before the scheduled follow up period.

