8.2.7 Pregnancy

Details of all pregnancies in female participants and female partners of male participants will be collected after first dose of study drug and until 30 days after the last dose as outlined in Section 10.5.3. If a pregnancy in a female participant or the partner of a male participant is reported, the Investigator should inform the Sponsor within 24 hours of learning of the pregnancy and should follow the procedures outlined in Section 10.5.3. Abnormal pregnancy outcomes (eg, spontaneous abortion, fetal death, stillbirth, congenital anomalies, ectopic pregnancy) are considered SAEs.

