10.3.5.2 Events that Occur after Study Drug Initiation

After initiation of study drug, AESIs, SAEs, and pregnancies will be reported until end of study at Day 115 or Early Termination. Investigators should record all case details that can be gathered immediately (ie, within 24 hours after learning of the event) on the Adverse Event eCRF and submit the report via the electronic data capture (EDC) system. A report will be generated and sent to Safety Risk Management by the EDC system.

In the event that the EDC system is unavailable, the Serious Adverse Event/Adverse Event of Special Interest Reporting Form provided to Investigators should be completed and submitted immediately (ie, ≤24 hours after learning of the event), either by faxing or by scanning and emailing the form using the fax number or email address provided in Section 10.3.5.1. Once the EDC system is available, all information will need to be entered and submitted via the EDC system.

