#### 9.1. Adverse Events

A TEAE is defined as an AE that occurs during or after the first study drug administration and up to and including the follow-up visit. For partially missing dates, the imputation rules described in Section 4.1 will be followed, and imputed dates will be used to determine whether an AE is treatment-emergent. If the start date is completely missing, then the AE is considered treatment-emergent if the end date (imputed or not) is on or after the date of first dose. If both the start and end dates are completely missing, then the AE is considered treatment-emergent.

All AEs will be coded using the latest MedDRA version available at the end of the study.

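### Protocol 8.2.6.1 and 10.3.5.2 let safety reporting end at Early Termination, contradicting the follow-up window used elsewhere; for early leavers, up to about 31 days after last dose may go unreported

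*Protocol*

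**What the plan says.** Two protocol sections allow reporting to end at Early Termination:

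- Section 8.2.6.1, for AEs in general: "all AEs will be reported until end of study at the Follow-up Visit or until an Early Termination visit".
- Section 10.3.5.2, for the expedited categories: "AESIs, SAEs, and pregnancies will be reported until end of study at Day 115 or Early Termination".

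The End of Study definition in 4.4 likewise accepts an Early Termination Visit as an alternative to the Follow-up Visit.

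Other parts of the plan set a later end:

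- Schedule of Assessments, footnote i (repeated in the SAP appendix): "all adverse events will be collected and reported to the Sponsor until the last follow-up visit".
- SAP 9.1 counts an event as treatment-emergent from first dose "up to and including the follow-up visit". The protocol synopsis and 9.3.2 use the same end-point.
- Estimands 2a and 2b (TEAEs and SAEs) take the at-risk period to the end of follow-up, in protocol Section 3.0 and in the SAP.
- Protocol 8.2.7 collects pregnancies "until 30 days after the last dose".
- Protocol 7.1, for a participant who has already had the Early Termination visit: "The scheduled safety follow-up visit will also be performed, if possible". Section 7.2 keeps a safety follow-up visit after withdrawal from the study, timed from the last dose.

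**The concern.** The same data have two different end-points. Section 8.2.6.1 is the section that sets the AE collection period, and 10.3.5.2 governs expedited reporting, so a site could reasonably treat them as controlling. It could then hold the follow-up visit that 7.1 and 7.2 keep, yet regard new events as outside the reporting period.

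The incidence proportions of TEAEs and SAEs are primary safety endpoints. An incidence proportion makes no allowance for unequal observation time. If early leavers are observed for less time after their last dose than completers, their events are under-counted. If leaving differs by arm, the under-count differs too. The backstop in 8.2.6.1 for events after a participant leaves covers only SAEs that the investigator happens to learn of and judges related. Non-serious AEs and unrelated SAEs are not covered, though both count in the endpoints.

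**Working it through.** **1. The plan's own timeline.** Protocol 6.3 gives 28 + 84 + 30 = 142 days, which reproduces its stated total. Last dose is Day 84 and the Follow-up Visit is Day 115 ±7.

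- Post-dose window: 115 − 84 = 31 days.
- With the visit window: 108 − 84 = 24 days to 122 − 84 = 38 days.

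For an early leaver I take the safety follow-up visit to fall the same 31 days after last dose. This is how 7.2 times it; 7.1 does not say.

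**2. Days outside the literal cut-off.** Section 7.1 wants Early Termination procedures promptly after stopping drug but gives no number of days. The gaps below are assumed.

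| Early Termination, days after last dose | Days unreported of 31 | Share |
|---|---|---|
| 0 | 31 | 100% |
| 3 | 28 | 90% |
| 7 | 24 | 77% |
| 14 | 17 | 55% |

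**3. How many participants.** The documents give no early-leaving rate. At an assumed 5%, 10%, 15% or 20% of 225, about 11, 23, 34 or 45 participants are affected (2 to 9 per arm of 45). With Early Termination on the day of last dose, the unreported time is 225 × rate × 31 = about 349, 698, 1,046 or 1,395 person-days. If the mean stop is Day 42 (assumed), total at-risk time at 10% is 202.5 × 115 + 22.5 × 73 = 24,930 days, so the share is 698/24,930 = 2.8%. Over the four rates the share runs from 1.4% to 5.8%.

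**4. Effect on the TEAE proportion.** Assume a constant hazard, 50% with a TEAE by Day 115, a stop at Day 42, and Early Termination on that day.

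- Hazard: ln 2 / 115 = 0.00603 per day.
- Event-free at Day 42: exp(−0.00603 × 42) = 0.776.
- First TEAE in the next 31 days, if event-free: 1 − exp(−0.00603 × 31) = 0.170.
- Missed first TEAEs per early leaver: 0.776 × 0.170 = 0.132.
- At 10% leaving: 4.5 × 0.132 = 0.6 participants per arm of 45, or 1.3 percentage points.
- At 5% and 20% leaving: 0.7 and 2.6 points.
- If one arm loses 10% and another 5%, the distortion of the difference is 1.3 − 0.7, about 0.7 points before rounding (0.05 × 0.132).

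Varying the assumed TEAE rate at 10% leaving:

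- 30% by Day 115: hazard −ln 0.7 / 115 = 0.00310; 0.878 × 0.092 = 0.080, or 0.8 points.
- 70% by Day 115: hazard −ln 0.3 / 115 = 0.01047; 0.644 × 0.277 = 0.179, or 1.8 points.

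**5. What alignment restores.** For a Day 42 stop, follow-up ends near Day 42 + 31 = 73, against Day 115 for completers. The literal cut-off leaves a shortfall of 115 − 42 = 73 days. Aligning the sections recovers 31 of these; the other 42 arise from stopping early and remain.

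**6. Pregnancies.** A follow-up visit at Day 108 is 24 days after a Day 84 last dose, short of the 30 days in 8.2.7. Tying pregnancy reporting to the visit alone would leave that conflict in place.

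**The case against.** A reader might infer that early leavers simply lose their post-treatment safety window, or that events after Early Termination cannot be reported. The protocol as a whole does not prescribe that. Sections 7.1 and 7.2 keep the follow-up visit, the Schedule marks AE monitoring at it, and footnote i collects AEs up to it. Section 8.2.6.1 itself has investigators ask about AEs at every contact. Its cut-off can also be read as whichever visit ends participation. Pregnancies have their own rule in 8.2.7, and related SAEs learned of later remain notifiable.

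The bias argument is also weakest for those who stop because of tolerability. Under 7.1, participants who stop for an AE or laboratory abnormality continue at the regular visits until it resolves or stabilises. Those who stop for an AE that began after first dose already count as having a TEAE.

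Protocol 9.3 calls the analysis descriptive and exploratory, and SAP 9.1.1 plans counts and percentages with no between-arm test of AEs.

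All of this stands, and it limits the consequence. It does not remove the contradiction. The continued visits cover only some early leavers and only for a time, the 7.1 follow-up visit is held only where feasible, and the post-discharge provision leaves out non-serious and unrelated events.

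**Conclusion.** The contradiction is real and should be corrected: two reporting rules name an earlier end-point than footnote i, the TEAE definition, Estimands 2a and 2b, 8.2.7, and the visits kept by 7.1 and 7.2. The all-AE cut-off appears only in 8.2.6.1, and the one for pregnancies only in 10.3.5.2.

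The consequence is a risk under a literal reading: up to about 31 days after last dose unreported per early leaver. The likely effect on TEAE incidence is small, about 1.3 percentage points per arm in the central scenario and 0.7 to 2.6 points as early leaving goes from 5% to 20%. These figures rest on an assumed TEAE rate, leaving rate, stopping day and constant hazard, none of which the documents supply. They also place Early Termination on the day of last dose and suppose that every site applies the cut-off, so they are upper values for each scenario.

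Estimand 2c is not part of this point. The SAP Section 8 table ends its period at treatment discontinuation, whereas protocol Section 3.0 and SAP 2.1 carry it to the end of follow-up. That is a separate inconsistency.

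**What to change.** Delete the Early Termination cut-off from 8.2.6.1 and 10.3.5.2, and state instead:

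- AEs, AESIs and SAEs are reported through the safety follow-up visit for all participants, including after Early Termination, unless consent is withdrawn.
- Pregnancies are reported through the later of that visit and 30 days after last dose, consistent with 8.2.7.

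The cost is two protocol sentences and a note to sites. No visit is added, and the TEAE definition and Estimands 2a and 2b stay as they are. Because early leavers will still have less total time at risk than completers, the change should not be described as equalising exposure.

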8.2.6.2 Method of Detecting AEs

The method of recording, evaluating, and assessing causality of AEs and the procedures for completing and transmitting SAE reports are provided in Section 10.3.4 and Section 10.3.5.

Care will be taken not to introduce bias when detecting AEs. Open-ended and nonleading verbal questioning of the participant is the preferred method to inquire about AE occurrences.

Examples of nonleading questions include the following:

"How have you felt since your last clinic visit?"

"Have you had any new or changed health problems since you were last here?"

